4.2 POPULATIONS

4.2.1 Study population

The study population will include all patients with early-stage HER2+ breast cancer having received at least one dose of neratinib as an extended adjuvant therapy in the context of the EAP in Europe between August 01, 2017 and December 31, 2020.

4.2.1.1 Inclusion criteria

Patients will be eligible for inclusion if they fulfill ALL of the following criteria:

- Age \geq 18 years at neratinib treatment initiation
- Having received at least one initial dose of neratinib as an extended adjuvant therapy for the treatment of early-stage HER2+ breast cancer, in the context of the EAP in Europe, and between August 01, 2017 and December 31, 2020
- Patients (or next of kin/legal representative, if applicable) who provide written informed consent or non-opposition.

Note: Given the retrospective nature of the study, for deceased or lost to follow-up subjects, where a signed informed consent is required, the informed consent may be obtained from a next of kin / legal representative, or an ICF waiver will apply, depending on approval by Ethics Committees and/or local regulations.

4.2.1.2 Exclusion criteria

Eligibility for treatment with neratinib was assessed at the time of early access drug supply provision. For the purposes of this retrospective data collection, it is desirable that eligibility criteria are the least restrictive possible. Therefore, there are no exclusion criteria for patients in this study.

4.2.2 Patient selection and follow-up

4.2.2.1 Study centers

The target countries for study participation will include Belgium, Croatia, France, Italy, and Spain. Only study centers where treating physicians have treated at least one patient with neratinib as an

 Pierre Fabre TEMP CQA 0092 V 2.0	Template to use for writing Corporate document, except Corporate policy and form, WORD in english	Page 14/ 29
Owning site : CORPORATE QA		

extended adjuvant therapy for early stage HER2+ breast cancer in the context of the European EAP between August 01, 2017 and December 31, 2020 (41 centers) will be approached to participate in this study. All centers from the list will be invited to participate in the feasibility phase. All responses, whether positive or negative, will be tracked and recorded by IQVIA.

4.2.2.2 Patient selection

- Study initiation, patient selection, and data abstraction are planned to start in 2022
- All patients \geq 18 years old who received at least one initial dose of neratinib as part of the EAP in Europe, between August 01, 2017 and December 31, 2020, will be invited to participate in this observational study
- After verification of the eligibility criteria, the investigator or qualified designee will inform the patient (or his/her next of kin or legal representative, in the case of deceased patients) about:
 - The study objectives
 - The possibility of refusing to participate or terminating his/her participation in the study, without any prejudice to the relationship with the investigator and the patient's medical care
 - Processing of personal data that will be collected during this study and the rights of access, opposition, and rectification to this data.

The patient (or his/her next of kin or legal representative, in the case of deceased patients) will be provided with a written or electronic information sheet about the study prior to data abstraction from patient records. If the patient (or his/her legal representative or next of kin) agrees to participate, he/she (or his/her next of kin or legal representative) will be asked to provide their written informed consent or non-opposition to study participation to the investigator (depending on local regulations), which will be documented in the patient's medical file. Wherever applicable, an ICF waiver will be obtained, depending on approval by Ethics Committees and/or local regulations. The patient (or his/her next of kin/legal representative) may, at any time, object to the use of the patient's data, in the context of research.

In the singular case of France, it is permissible to merely obtain a non-opposition in order to enrol a patient in observational studies. In order to do this, it is sufficient to inform potential subjects (or their next-of-kin/legal representative) about the study by post. Thus, participating centres will be able to send patient information sheets via registered post with an acknowledgement of receipt. Patients will have 4 weeks to oppose data collection following reception of the letter. Even if no formal opposition is received, their data may be collected for the study. Patients will also be informed that they may oppose data collection at any time during the study without any repercussions on their ongoing care. In the case of opposition to the collection of their data at any point during the study, their case would be considered as withdrawn.

The investigator will document, in the patient's medical file, the patient's (or the next-of-kin's/ legal representative's) informed consent, refusal, non-opposition or opposition to study participation, before data abstraction is performed.

Since there are no anticipated benefits or detriments to taking part in this study, patients refusing to participate will be treated identically to those enrolled in the study, as per the current standard of care.

 Pierre Fabre TEMP CQA 0092 V2.0 Owning site : CORPORATE QA	Template to use for writing Corporate document, except Corporate policy and form, WORD in english	Page 15/ 29
--	--	-------------

A screening log will be maintained at each center for all eligible patients, where sex, age category and survival status (dead/alive/lost to follow-up) will be collected. The reason(s) for refusal to participate will be recorded for those who declined to participate in the study.

Data that will be collected upon study inclusion are detailed in section 4.3 below.

4.2.2.3 Patient follow-up

- Initiation of neratinib treatment as an extended adjuvant therapy within the European EAP is the index date for each eligible patient.
- The maximum follow-up duration is until the end of the study observation period (study entry date), up to which all available data will be collected.
- Data will be extracted from existing medical records by the investigator or qualified designee as per standard clinical practice, from baseline till study entry date, death, study withdrawal, or loss to follow-up.
- Data for each patient will be recorded by the investigator or qualified designee in electronic case report forms (eCRF). Following study inclusion, data will be abstracted from the medical charts until study entry date as detailed in section 4.3, and summarized in the data collection schedule (Table 1).

 Pierre Fabre <code>TEMP_CQA_0092_V2.0</code> Owning site : CORPORATE QA	Template to use for writing Corporate document, except Corporate policy and form, WORD in english	
		Page 16/ 29

Table 1: Data collection schedule for eligible patients in the NEAR study

The eligible patients' data from baseline until the end of the study observation period will be collected during data abstraction period (from study entry date to end date of data abstraction).

Data	Baseline Period	Start of Neratinib Treatment	Treatment Phase	End of Treatment (EOT)	Available Tumor / Survival assessment post EOT
Treatment history before neratinib initiation (section 4.3.1)	X				
Patient characteristics at primary diagnosis of breast cancer/neratinib initiation (section 4.3.1)		X			
Neratinib treatment details (section 4.3.2)		X	X	X	
Concomitant treatments with neratinib (section 4.3.2)		X	X	X	
Adverse Events* (section 4.3.2)		X	X	X	
Breast cancer recurrence / Survival status until the end of the study observation period				X	X
Reasons for neratinib discontinuation					X

* For the safety outcomes, only relevant AEs, that occurred during neratinib use (until the end of the study observation period) (section 4.3.2) will be assessed.

 Pierre Fabre TEMP CQA 0092 V2.0 Owning site : CORPORATE QA	Template to use for writing Corporate document, except Corporate policy and form, WORD in english	Page 17 / 29
--	--	--------------

4.3 STUDY OUTCOMES

The outcomes of this retrospective, observational study is purely descriptive. They aim to summarize the characteristics of patients receiving neratinib in the context of the EAP in Europe, and to describe the use of neratinib in real-life, as well as the associated adverse effects of this medication.

4.3.1 Primary outcome

Demographics and clinical profile of patients with early-stage HER2+ breast cancer will be described, for the full analysis set and by subgroup(s) of interest, if the number of patients allow, (see section 4.3.4). The following baseline data will be collected at study entry:

1. Patient demographic and clinical characteristics at neratinib initiation, unless stated otherwise:
 - Age (year of birth), gender, weight, height, body mass index (BMI)
 - Performance status using the Eastern Cooperative Oncology Group (ECOG), Karnofsky or any other scoring system at primary diagnosis of breast cancer and at neratinib initiation
 - Employment status
 - Date of primary diagnosis of breast cancer
 - Menopausal status at primary diagnosis of breast cancer
 - Location of the primary tumor at primary diagnosis of breast cancer
 - Histology of primary diagnosis of breast cancer
 - Histological grade (Grade 1, Grade 2, Grade 3)
 - Histological subtype (Ductal, Lobular, Other etc.)
 - Breast Cancer stage at the time of primary diagnosis, using the Tumor/Node/Metastasis (TNM) classification system (I, II, III)¹⁹
 - Pathological Stage (American Joint Committee on Cancer classification) at the time of primary diagnosis
 - Relevant comorbidities at neratinib initiation, including, but not limited to the following:
 - Renal disease
 - Liver disease
 - Gastro-intestinal disorders
 - Cardiovascular conditions
 - Skin and subcutaneous tissue disorders
 - Diabetes (Type I or II)
 - Tumor biology
 - HR status (estrogen receptor [ER] and progesterone receptor [PgR] status)
 - HER2 overexpression/amplification
 - Ki-67 (if available)
 - Grading

4.3.2 Secondary outcomes

1. Neratinib treatment patterns will be described, including time to initiation after a trastuzumab based treatment, treatment dose, treatment duration, permanent and temporary discontinuation and reasons for treatment discontinuation or switch at the end of neratinib treatment as an extended adjuvant therapy for early-stage HER2+ breast cancer. All relevant information up to the end of the study observation period will be collected. Additionally, treatment

 Pierre Fabre TEMP CQA 0092 V2.0 Owning site : CORPORATE QA	Template to use for writing Corporate document, except Corporate policy and form, WORD in english	Page 18/ 29
--	--	-------------

persistence, median time to permanent discontinuation and median time to first dosage modification will also be evaluated via Kaplan-Meier estimates.

The following data will be collected to describe treatment patterns during neratinib use as an extended adjuvant therapy:

- End date of preceding trastuzumab treatment
- Initial dosage, Start and end date (if applicable)
- Dosage modifications (if applicable): dates, new dosage, reason for modification
- Neratinib discontinuation: date and reason for permanent or temporary discontinuation, duration of temporary discontinuation, subsequent treatment after discontinuation
- Subsequent treatment(s) upon disease recurrence or treatment discontinuation
- Concomitant endocrine therapy (for HR+ patients): type, start date, stop date
- Others concomitant treatment (if any): type, start date, stop date
- Corrective treatment for relevant AEs

2. Treatment history for breast cancer before neratinib initiation will be described. The following data will be collected:

- Prior anti-cancer drugs/therapies/procedures for breast cancer: type, medication name, start date and stop date
- Type of surgeries and date
- Radiotherapy after surgery (Yes/No): date and area
- Prior neoadjuvant and/or adjuvant anti HER2-directed therapy(ies) (including trastuzumab): type, start date and stop date
- Outcome of neoadjuvant/ treatment (if applicable): pathologic complete response (pCR) or no pCR
- Concomitant endocrine therapy

3. Frequency of relevant AEs during treatment with neratinib as an extended adjuvant therapy will be determined. Relevant AEs will be defined as all SAEs or AEs leading to dose adaptation or treatment discontinuation, and AEs of interest.

The following are some AEs of interest: occurrence of diarrhea (onset/resolution dates, maximum grade, actions taken), gastro-intestinal toxicity (nausea, vomiting, abdominal pain, constipation), hepatic disorders, cardiac disorders, pulmonary disorders, pancreatitis, and reproductive and developmental disorders.

All relevant AE data will be extracted from medical records and mapped into the Medical Dictionary for Regulatory Activities (MedDRA) and grouped by system organ class (SOC) and preferred term (PT).

 Pierre Fabre TEMP CQA 0092 V2.0 Owning site : CORPORATE QA	Template to use for writing Corporate document, except Corporate policy and form, WORD in english	Page 19/ 29
--	--	-------------

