Neratinib (Nerlynx®), an orally available, irreversible tyrosine kinase inhibitor (TKI), was approved by the Food and Drug Administration (FDA) in 2017 and in the European Union (EU) in 2018. In the EU, Neratinib's approved indication is for extended adjuvant therapy of adult patients with early-stage Hormone Receptor-positive (HR+) HER2-overexpressed/amplified breast cancer and who completed prior adjuvant trastuzumab-based therapy less than one year ago. The recommended dose of neratinib is 240 mg (six 40 mg tablets) taken orally once daily, continuously for one year¹⁵. Comparatively, the FDA approved indication applies to a broader profile of patients, where neratinib as a single agent is approved for the extended adjuvant

 Pierre Fabre TEMP CQA 0092 V2.0 Owning site : CORPORATE QA	Template to use for writing Corporate document, except Corporate policy and form, WORD in english	Page 10/29
--	--	------------

therapy of adult patients with early-stage HER2-positive breast cancer, to follow adjuvant trastuzumab-based therapy. Nothing is specified in terms of HR status or the length of prior adjuvant trastuzumab-based therapy.

Certain patients may have received neratinib as per the FDA indication, as part of the EAP in Europe.

Results of the ExteNET trial showed that patients with early-stage HER2+ breast cancer receiving one year of extended adjuvant therapy with oral neratinib (within a year of standard of care adjuvant trastuzumab), had significant improvement in the 2-year iDFS rate compared to placebo (93.9% versus 91.3%, respectively; hazard ratio, 0.67; 95% Confidence Interval (CI), 0.50–0.91; $p = 0.0017$)¹⁶. A 5-year follow-up reported similar results (hazard ratio 0.73; 95% CI 0.57–0.92; $p=0.008$)¹⁷. Furthermore, greater improvement in iDFS was observed in HER2+ patients with HR+ breast cancer¹⁶⁻¹⁸.

An Early access program (EAP) was initiated in Europe in 2017, providing access to neratinib to individual patients following specific criteria outside of a clinical trial. This program is currently ongoing in certain European countries, awaiting product reimbursement. This study will provide real-world data to characterize the profile of patients treated with neratinib, their previous medical history, the conditions for using neratinib and its profile in terms of safety and effectiveness as an extended adjuvant therapy. The profile of patients may be more diverse compared to those enrolled in the ExteNET trial.

Rationale

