12 SECONDARY OUTCOMES

12.1 Neratinib Treatment Patterns

Neratinib treatment patterns will be described as frequencies and percentages or summary statistics, as appropriate, for FAS and by subgroup EU label; Pathologic stage; Residual disease after neoadjuvant treatment; Risk profile; Previous adjuvant or neoadjuvant therapy and Prior transtuzumab-based regimen overall and last treatment (Section 8.4).

For duration of neratinib treatment calculations, the date of first and last neratinib administration will be taken from the eCRF “Neratinib Treatment” form, variables “Neratinib Initiation date” and “Definitive discontinuation date” respectively. Interruptions, compliance, and dose changes are not considered for duration of neratinib treatment.

Neratinib treatment initiation details:

- Time from breast cancer diagnosis to neratinib initiation (months), calculated as:
 - $(Date\ of\ first\ neratinib\ administration - Date\ of\ diagnosis + 1) / 30.4$
- Time from completion of adjuvant trastuzumab-based therapy to neratinib initiation (months), calculated as:
 - $(Date\ of\ first\ neratinib\ administration - Date\ of\ completion\ of\ adjuvant\ trastuzumab-based\ therapy + 1) / 30.4$
- Performance status scale used at neratinib initiation: ECOG, Karnofsky, Other
 - If ECOG: 0, 1, 2, 3, 4, Unavailable
 - If Karnofsky: 100, 90, 80, 70, 60, 50, 40, 30, 20, 10, Unavailable and 90-100, 70-80, 50-60, 30-40, 10-20, Unavailable
- Performance status computed ECOG score (based on Table 3): 0, 1, 2, 3, 4, Unavailable
- Duration of neratinib treatment (months), calculated as:
 - For discontinued treatment,
 $(Date\ of\ last\ administration - Date\ of\ first\ administration + 1) / 30.4$

Document: ZZA65950_NEAR_SAP_v2.0

Author: [name]

Version Number: 2.0

Version Date: 22SEP2023

- For ongoing treatment, (*EOB date - Start date + 1*)
- Duration of neratinib treatment (categorized): ≤ 3 months, > 3 months to < 12 months, 12 months, >12 months
- Initial daily dosage (mg)
- Initial daily dose (mg), category: 40mg, 80mg, 120mg, 160mg, 200mg, 240mg, ...; and <240mg, 240mg, >240mg

Treatment modifications (dosage changes):

- Number and percentage of patients with at least one neratinib treatment modification. Percentage computed among FAS.
- Number of temporary modifications by patient
- Temporary modifications per patient category: 1, 2, >2. Percentage computed among FAS patients with at least one neratinib treatment modification.

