12.4 Adverse Events

In this study relevant AEs that occurred between index date and 30 days after Neratinib discontinuation, study entry date or death, whichever occurs first, are collected in the eCRF and will be analyzed. Relevant AEs are defined as all SAEs, AEs leading to dose adaptation or treatment discontinuation, and AEs of interest.

The following are AEs of interest:

- Occurrence of diarrhea
- Gastro-intestinal disorder
- Hepatic disorders
- Cardiac disorders
- Pulmonary disorders
- Pancreatitis
- Reproductive and developmental disorders

SAEs will be identified as those reported as “Serious” on the Adverse Events page of the eCRF, AEs leading to treatment dose change (increase/decrease) or permanent discontinuation of neratinib will be identified from the action taken in the AE details page of the eCRF.

Adverse Events (AEs) will be coded using MedDRA version 24.1.

See Appendix 1 for handling of partial dates for AEs.

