12.4.1 Relevant AEs

Relevant AEs will be summarized as number and percentage of subjects experiencing the event and number of events reported. The analysis of all relevant AEs recorded in the eCRF will be presented by the following variables for FAS and by subgroup EU label; Prior trastuzumab-based regimen overall and last treatment:

- Any relevant AE
- Any AEs of special interest
 - by interest type: Occurrence of diarrhea, Gastro-intestinal disorder, Pulmonary disorder, Reproductive and developmental disorder, Hepatic disorder, Cardiac disorder, Pancreatitis
- Any SAEs
 - by SAE type: Death, Life threatening, Hospitalization due to AE – initial or prolonged, Congenital diseases/abnormalities, Disability/ incapacity and Other clinically significant conditions
- By Severity: Grade 1, 2, 3, 4 and 5
- By Action taken: None, Treatment dose increased, Treatment dose decreased, Treatment discontinued, Corrective treatment
- By Outcome: Recovered, Recovered with sequelae, Recovering, Not recovered, Death, Unknown
 - By Causal relationship to neratinib treatment: Reasonable possibility, Not reasonable possibility

If number of patients is large enough, the following analyses will be performed :

- Relevant AEs by SOC and PT for each Severity grade
- Relevant AEs by SOC and PT for each Severity grade by subgroup Prior trastuzumab-based regimen subgroup
- Relevant AEs by SOC and PT for each Severity grade, for patients with treatment discontinuation reason “Patient wish”

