12.4.2 Occurrence of Diarrhea

The occurrence of diarrhea is an AE of particular interest, thus, the following variables will be summarized as number and percentage of subjects experiencing the event and number of events reported for FAS and by subgroup EU label; Prior trastuzumab-based regimen overall and last

Document: ZZA65950_NEAR_SAP_v2.0

Author: [name]

Version Number: 2.0

Version Date: 22SEP2023

treatment; Concomitant Corrective Antidiarrheal Treatment and Concomitant Prophylaxis Antidiarrheal Treatment (section 8.4):

- Any Occurrence of Diarrhea AE
- Any Occurrence of Diarrhea SAEs
 - by SAE type: Death, Life threatening, Hospitalization due to AE – initial or prolonged, Congenital diseases/abnormalities, Disability/ incapacity and Other clinically significant conditions
- By Severity: Grade 1, 2, 3, 4 and 5
- Occurrence of diarrhea episodes by Severity: Grade 1, 2, 3, 4 and 5
- By Action taken: None, Treatment dose increased, Treatment dose decreased, Treatment discontinued, Corrective treatment
- By Outcome: Recovered, Recovered with sequelae, Recovering, Not recovered, Death, Unknown
- By Causal relationship to neratinib treatment: Reasonable possibility, Not reasonable possibility

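### The relevant-AE tables give percentages and event counts without patient-time, so columns with different early stopping cannot be read at equal exposure

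*Protocol*

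**What the plan says.** Protocol 4.3.2, item 3, names the outcome: "Frequency of relevant AEs during treatment with neratinib as an extended adjuvant therapy will be determined". The analysis is in the SAP. Section 12.4.1 states: "Relevant AEs will be summarized as number and percentage of subjects experiencing the event and number of events reported". The tables are given for the FAS, by EU label status, and by prior trastuzumab-based regimen (overall and last treatment). Section 12.4.2 has diarrhea "summarized as number and percentage of subjects experiencing the event and number of events reported for FAS and by subgroup EU label" and adds columns for prior regimen and for corrective and prophylactic antidiarrheal treatment.

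Time at risk differs between patients. Protocol 4.2.1.1 asks only for "Having received at least one initial dose of neratinib as an extended adjuvant therapy", while Protocol section 2 describes neratinib as "taken orally once daily, continuously for one year". SAP 12.1 plans the categories "Duration of neratinib treatment (categorized): ≤ 3 months, > 3 months to < 12 months, 12 months, >12 months". SAP 12.4 collects "relevant AEs that occurred between index date and 30 days after Neratinib discontinuation, study entry date or death, whichever occurs first", so each patient's window closes according to that patient's own stop date.

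Neither document plans an exposure-adjusted rate, time to first AE or cumulative incidence for any AE. Kaplan-Meier is kept for treatment patterns (SAP 12.1) and the exploratory outcomes (SAP 13.2).

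**The concern.** A patient who stops in month 1 counts in the denominator exactly like one treated for 12 months, and the event count is printed beside no measure of exposure. For AEs that can arise at any point in the course, such as hepatic, cardiac or pulmonary disorders, a column with more early stopping will show a lower percentage even when the monthly risk is the same. Readers will look across the EU-label and prior-regimen columns and may take a difference in time on drug for a difference in tolerability.

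**Working it through.** **Inputs.** Neither document states an AE rate or an early-stopping rate, so there is no figure of the plan's to reproduce. All rates below are assumptions.

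**Step 1: is short exposure caused by the data cut-off?** The last possible index date is 31 December 2020 and the cut-off is 05 July 2022 (SAP 7.1, 7.5). That is 551 days, and (551 + 1)/30.4 = 18.2 months. The cut-off cannot truncate a one-year course begun in the window. Short exposure comes from stopping, death or loss to follow-up.

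**Step 2: two columns with the same hazard.** Let the AE hazard be h per month, with a fraction e stopping at 2 months for reasons unrelated to the AE and the rest treated for 12. Ignoring the 30-day window:

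crude % = (1 − e)(1 − exp(−12h)) + e(1 − exp(−2h))

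At h = 0.02 the two risks are 1 − exp(−0.24) = 21.3% and 1 − exp(−0.04) = 3.9%.

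- e = 0.2: 0.8 × 0.2134 + 0.2 × 0.0392 = 17.9%
- e = 0.4: 0.6 × 0.2134 + 0.4 × 0.0392 = 14.4%
- e = 0.5: 0.5 × 0.2134 + 0.5 × 0.0392 = 12.6%

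The 20% versus 50% contrast is 9.4% versus 6.6% at h = 0.01, and 38.0% versus 27.3% at h = 0.05. Letting the hazard run one further month, to mimic the 30-day window, gives 19.5% versus 14.4% at h = 0.02.

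**Step 3: dependence on onset and on the reason for stopping.** Assume a 12-month risk of 30% and a constant rate μ of non-AE stopping, with a fraction d stopped by month 12, so μ = −ln(1 − d)/12. For constant h = −ln(0.7)/12, crude % = h/(h + μ) × (1 − 0.7(1 − d)). For d = 0.2 this is 0.615 × 0.44 = 27.1%. The other onset patterns were integrated numerically.

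| AE onset | d = 20% | d = 40% | d = 60% |
|---|---|---|---|
| Constant | 27.1% | 23.8% | 20.2% |
| Early (mean 1 month) | 29.5% | 28.9% | 28.1% |
| Late (after month 6) | 25.5% | 20.7% | 15.4% |

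If the AE itself is the only cause of stopping, the crude value is 30.0% and nothing is lost.

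**Step 4: the denominator must match the AE window.** Take h = 0.02, count first events to one month after stopping, but count patient-time only to the last dose. Time at risk to first event over t months is (1 − exp(−ht))/h.

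- 2-month stoppers: 0.0582/1.961 = 2.97 per 100 patient-months
- 12-month completers: 0.2289/10.669 = 2.15 per 100 patient-months

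The true hazard is 2.00 in both, so this mismatch makes early stoppers look worse. With time at risk over the same window, the results are 0.0582/2.912 = 2.00 and 0.2289/11.447 = 2.00.

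**The case against.** The strongest reply is that the crude percentage answers the question asked. The outcome is frequency during treatment, in a study that Protocol 4.3 calls descriptive only, and Step 1 shows that follow-up is long enough to observe it. A reader might infer that the plan understates AE risk. The documents do not support this: risk over a full year without early stopping is not a stated target, and early stopping is part of the use being described. This part of the objection stands.

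A reader might also infer that the subgroup columns cannot be compared at all. That is too strong. SAP 12.1 already tabulates treatment duration by EU label and by both prior-regimen groupings, the same subgroups as the relevant-AE tables, and shows permanent discontinuation by Kaplan-Meier for the prophylaxis subgroup. Number of patients times mean duration gives rough patient-months. It does not give time at risk to a first event or cover the 30 days after stopping, and it sits in a separate table. The corrective-antidiarrheal columns have no exposure output.

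Three further points limit the weight of the concern. The pertuzumab and T-DM1 rationale (Protocol sections 1 and 2) concerns clinical profile and effectiveness, with safety described in addition, and no AE test between regimens is planned. AEs leading to discontinuation are themselves relevant AEs, so those patients count as cases in the any-relevant-AE row, although rows for other AEs still lose exposure time. Finally, with 120 patients (SAP 4.2), two groups assumed to have 40 each give a 95% half-width of about ±16 points for 17.9% versus 12.6% (±13 with 60 each). That exceeds the artefact of about 5 points. Imprecision does not remove a systematic component, but it argues for modest priority.

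**Conclusion.** The point holds as a reporting gap. AE frequency is planned without patient-time although time at risk varies widely, and nothing in the AE tables lets a reader separate less time on drug from lower risk. The percentage remains a valid figure for use as it occurred.

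The distortion between columns depends on early stopping differing between them for reasons other than the AE in question. In the illustration it is about 5 points at 2% per month (2.8 points at 1%, 10.7 at 5%). It is small for early-onset AEs, nil where only the AE causes stopping, and largest for late-onset AEs: with 60% stopping early, the crude figure is about half the full-course risk. These sizes rest on assumed hazards and stopping patterns. This is a cheap improvement, not a defect that invalidates the outcome.

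**What to change.** 1. Reconcile the AE window. The footnote to Protocol Table 1 limits AEs to the time of neratinib use, while SAP 12.4 adds 30 days. Patient-time cannot be defined until the two agree.
2. In the tables of SAP 12.4.1 and 12.4.2, for the FAS and the EU-label and prior-regimen columns (and the prophylaxis columns for diarrhea), keep n (%) and add patient-months at risk over that same window.
3. Add patients with a first event per 100 patient-months (time ending at the first event) and total events per 100 patient-months, each with a 95% CI. The interval for total events must allow for repeat events within a patient. Show both for months 0-3 and after month 3.
4. Optionally, add cumulative incidence of the first AE with discontinuation and death as competing events.
5. State that rates do not make the corrective-antidiarrheal columns comparable, because those groups are defined by a response to the event itself.

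The cost is SAP wording and extra table columns, since treatment dates and AE start dates are already collected. Limits to state with the results: SAP 12.1 duration does not remove interruptions; AE dates missing both day and month are not imputed (SAP Appendix 1) and cannot be placed in a period; a rate assumes roughly constant risk within each period; and stopping driven by AEs is informative. The SAP 12.1 formula for ongoing treatment also lacks the division by 30.4 used for discontinued treatment, so patient-months should be computed directly from the dates.
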